## **6.8 CALCULATION OF TIME TO EVENT**

This Section describes the calculation of the time to event and the time that patients without an event were in the study (under risk).

Consistent with that approach, the respective time intervals determine the start and end for the derivation of occurrence of a specific event.

For those patients with an event, the time to event is calculated as:

<date of event> - < start date> + 1

For those patients without an event, the time at risk is calculated as:

<date of censoring> - < start date > + 1

### **6.8.1 Start date**

In general, the time to event will be derived from the date of randomisation.

If study drug administration happened before calling IXRS, the date of first drug administration will be used as start date.

For the endpoints of time-to-first-rescue-medication, time-to-first-hypoglycaemia and time-to-AE analysis (refer to [Section 7.8.1.3.2](#)), time to first silent MI and laboratory based endpoints, the date of first drug intake will be considered as starting point. (The use of a different start date is justified as the general definition of rescue medication applies only to the time after first study drug intake and general AEs (including hypoglycaemia) are analysed based on the concept of treatment emergent adverse events, refer to [Section 7.8.1.1.](#))

For composite endpoints that include component(s) using randomisation date and other component(s) using first drug intake date as start date, the time at risk for the composite will start with date of randomisation. For the individual components, the component specific start date is used.

### **6.8.2 Date of event**

For composite outcomes, e.g. time to 4P-MACE, 3P-MACE and time to the first occurrence of any of the components of the composite endpoint of all CEC confirmed adjudicated events, the earliest onset date of the corresponding components will be used. For fatal MI and fatal stroke the onset date of the event is used while for other CV deaths, the date of death is used.

The date determined by the adjudication committee will be used; this can be different from the investigator reported date.

For the endpoints of time to CV death, time to all-cause mortality and time to non CV death the respective death date will be used.

The time to the first silent MI is determined by the onset date of the adverse event defined as silent MI by the investigator.

For events with multiple episodes, such as hypoglycaemia, the onset date of the first episode will be used. The same applies to time-to-AE analysis.

For time to rescue medication, the first intake of rescue medication (or respectively increase in background medication dose) will be used.

The time to first occurrence of endpoints based on laboratory data, e.g. 'time to first new onset of macroalbuminuria' is determined by the date of the first laboratory measurement, in this example UACR measurement, that fulfils this condition.

### **6.8.3 Censoring**

*Primary, key secondary, secondary CV and tertiary CV endpoints (except stand-alone endpoints of CV death, all-cause mortality, non CV-death and silent MI) and time to first disabling or fatal stroke*

The underlying principle is that the censoring date should be the last date a patient was known to be free of an endpoint event (e.g. free of each component of the 4P-MACE).

Patients without occurrence of a specific endpoint (composite endpoint or individual components) will be considered censored at their last documented study visit\*.

\* This includes any dates as of

- adverse event/outcome event start dates (if non-fatal events),
- onset dates of adjudicated (confirmed and non-confirmed) events (if non-fatal event),
- date of PCI/CABG
- date of trial completion (defined as latest of date of last clinic visit, last telephone call, date of last contact if lost to follow-up).

Censoring is considered independent from study drug intake.  
Any information as permitted by local law will be used in the analyses.

#### *Time to first rescue medication (overall and protocol-defined)*

Patients without rescue medication intake that have prematurely and permanently stopped trial drug intake will be considered censored at their last documented study visit\* as described above.

Patients without rescue medication intake that have regularly completed trial drug intake until study end will be considered censored at their last treatment stop date.

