### 3.3.4 Removal of patients from therapy or assessments

#### 3.3.4.1 Removal of individual patients

This is a long-term safety outcome study and every effort should be made by the site staff to encourage patients to remain in the study and on study drug if medically safe. Patients who prematurely discontinue study drug should remain in the study and should be observed until study end, preferably at the study time points as pointed out in the [Flow Chart](#).

If a patient who prematurely discontinued study drug is not willing to return at the pre-defined regular visit schedule, at minimum a yearly telephone call (preferably every 6 months) and a telephone call at study end (through the patient or alternative person designated by the patient) will be required, to document the occurrence of outcome events and vital status. If possible, also other AE's and concomitant therapy changes since last visit should be recorded. Every attempt will be made by the investigator to ensure patients continue participating in the study during study drug interruptions and after discontinuation of study drug.

Patients who prematurely discontinue study medication are allowed to restart the study medication at any time if appropriate in the opinion of the investigator and if not contraindicated. In this study, patients are allowed to have multiple study drug interruptions. There is no limit on either the number of study drug interruptions or the maximum length of any study drug interruption. Investigators should routinely consider re-starting study drug at every visit following study drug discontinuation.

A patient could be instructed to stop the study drug only after discussion between sponsor representative and investigator, if eligibility criteria are being violated, or if the patient fails to comply with the protocol (e.g. non-attendance at study assessments). Early discontinuation of study medication is not a criterion for withdrawal of consent for participating in the study.

If determined by investigator as necessary for patient safety, new antidiabetic medication regimen can be started immediately after discontinuation of study treatment and must be recorded in the eCRF (see further details in [Section 4.2](#)).

If a patient becomes pregnant during the trial the study treatment will be stopped, the patient will be followed up during the study and until birth or otherwise termination of the pregnancy (see further details in [Section 5.2.2.2](#))

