#### Key Secondary endpoints

As key secondary endpoints will be analysed:

- 1) time to the first occurrence of any of the following adjudicated components of the composite endpoint: CV death (including fatal stroke and fatal MI), non-fatal MI (excluding silent MI), non-fatal stroke or hospitalisation for unstable angina pectoris.

- 2) composite endpoint of (treatment sustainability defined as the proportion of patients that are on study treatment at study end, that at Final Visit maintain glycaemic control ( $HbA1c \leq 7.0\%$ ) without need for rescue medication\* (between end of titration [Visit 6] and Final Visit) and patients without any moderate/severe hypoglycaemic episodes (between Visit 6 and Final Visit) and without  $> 2\%$  weight gain at Final Visit (between Visit 6 and Final Visit)).
- 3) composite endpoint of (treatment sustainability defined as the proportion of patients that are on study treatment at study end, that at Final Visit maintain glycaemic control ( $HbA1c \leq 7.0\%$ ) without need for rescue medication\* (between Visit 6 and Final Visit) and patients without  $> 2\%$  weight gain at Final Visit (between Visit 6 and Final Visit))

\* Any dose increase of anti-diabetic background medication or introduction of new anti-diabetic treatment during study medication treatment will be counted as rescue medication. Short term use of any insulin- up to two weeks - (e.g. during hospitalisation) won't count as rescue medication in the definition of treatment sustainability.

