*Other objectives are to compare HbA1c change from baseline, the incidence of hypoglycaemia, weight gain and treatment sustainability defined as the proportion of patients that are on study treatment at study end without need for rescue medication, that at Final Visit maintain glycaemic control ( $HbA1c \leq 7.0\%$ ).*

9.

Further aspects are clarified as follows:

1. In general rescue medication is not only considered during study medication intake. Rescue medication is defined as any dose increase of anti-diabetic background medication or introduction of new anti-diabetic treatment after first study medication intake until the time as specified in [Section 6.8](#). Short term use of any insulin- up to two weeks - will not count as rescue medication.
2. The endpoint of change from baseline to final visit is to be investigated for urinary albumin (secondary diabetes related endpoints). Any transition in albuminuria classes will be investigated based on UACR, in order to allow correction of albumin for creatinine concentration.
4. The censoring rules including those for 4P-MACE are described in detail in [Section 6.8.3](#).

In the following the changes and additional analyses as compared to the first signed Trial Statistical Analysis Plan from 22 JAN 2014 are described. This includes any changes based on clinical trial protocol amendments 5 and 6.

1. Based on the clinical trial protocol amendment 6 the definitions of the primary and first key secondary endpoints were updated throughout this document. Details on control of the type I error are defined in [Section 7.4.1](#). Following the exchange of the primary and first key secondary endpoint in CTP amendment 6, and the first interim analysis performed for time to first 4P-MACE, the allocation of alpha for the second interim analysis and the final analysis is defined in [Section 7.4.1](#).

Date of onset of silent MI and censoring of patients without silent MI was updated accordingly in [Section 6.8.2](#) and [6.8.3](#).

Derivation of time to event and censoring was updated accordingly in [Section 6.8.1](#), [6.8.2](#) and [6.8.3](#). The approach for the analyses of these endpoints was defined in [Section 7.6](#).

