#### Rescue medication in general:

Rescue medication is defined as any dose increase of anti-diabetic background medication (as compared to one day prior to first drug administration) or introduction of new anti-diabetic treatment, for insulin any new onset and intake for at least 15 days, starting from the date of first drug administration until the time as specified in [Section 6.8.3](#).

In general, any therapy with the start date equal to the date of first trial drug intake is considered as being taken after first trial drug intake.

If a patient switches to or adds protocol defined background medication at or after the date of first trial drug intake, this will be considered rescue medication. (The same applies for a change from metformin or alpha-glucosidase inhibitor to metformin + alpha-glucosidase inhibitor.)

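### Time to first rescue counts drugs that replace a stopped study drug, so unequal discontinuation alone can look like a rescue difference; an on-treatment companion analysis is needed

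*SAP*

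**What the plan says.** **Event.** SAP 5.2.1 gives the general definition: "Rescue medication is defined as any dose increase of anti-diabetic background medication", or the introduction of a new antidiabetic treatment, with insulin counted only if taken for at least 15 days. No glucose or HbA1c criterion is attached, and the reason for the change plays no part. The window runs "starting from the date of first drug administration until the time as specified in" SAP 6.8.3. The list of clarifications after the SAP introduction adds: "In general rescue medication is not only considered during study medication intake".

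**End of the window.** SAP 6.8.3 has two rules. For early stoppers: "Patients without rescue medication intake that have prematurely and permanently stopped trial drug intake will be considered censored at their last documented study visit". For the others: "Patients without rescue medication intake that have regularly completed trial drug intake until study end will be considered censored at their last treatment stop date". SAP 6.8 says that the same intervals govern whether an event occurred, so the percentage with rescue follows these rules as well.

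**Analysis.** SAP 7.5.2.2.4 plans Kaplan-Meier estimates, a log-rank test and the percentage with rescue on the treated set. SAP 7.5.2 makes all such analyses exploratory at two-sided 0.05. The 0-, 7- and 30-day censoring rules in 6.8.3 are not assigned to this endpoint.

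**Protocol.** Section 3.3.4.1 foresees that, where patient safety requires it, a "new antidiabetic medication regimen can be started immediately after discontinuation of study treatment". The footnote to the key secondary endpoints in Section 7.1 is narrower than the SAP: "Any dose increase of anti-diabetic background medication or introduction of new anti-diabetic treatment during study medication treatment will be counted as rescue medication".

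**The concern.** A patient who stops study drug early, for any reason, and is then given another antidiabetic drug has a rescue event. The same switch after regular completion is not counted. Which rule applies depends on discontinuation, which happens after randomisation and may differ by arm. The protocol itself makes a difference foreseeable: Section 2.3 names hypoglycaemia as a risk with glimepiride and a low risk with linagliptin, and Section 3.3.4.1 allows study drug to be stopped, permanently if needed, for repeated hypoglycaemia. A patient who stops because glucose is too low and then receives another drug would be counted as rescued.

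At stake is how one exploratory result is read. If one arm loses more patients from study drug, its curve shows more rescue even when the need for added therapy on study drug is the same in both arms. The curve and the percentage do not show how much comes from each source.

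**Working it through.** The documents give no rescue, discontinuation or replacement rate and no power statement for this endpoint, so there is no planned figure to reproduce.

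**Step 1: what is counted.**

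| New antidiabetic drug started | Counted as rescue? |
|---|---|
| On study drug | Yes |
| After premature permanent stop, up to last documented visit | Yes |
| After regular completion | No |

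**Step 2: inputs.** From the documents: 3000 patients per arm (Protocol synopsis), 2 years of accrual plus 5.4 years of follow-up (Protocol 7.6), log-rank test at two-sided 0.05 (SAP 7.5.2, 7.5.2.2.4). Assumed: rescue hazard on study drug λ = 0.05, 0.10 or 0.20 per year, identical in both arms; discontinuation d = 0.06 per year in one arm and 0.06, 0.05 or 0.04 in the other; share of stoppers given a replacement q = 0, 0.5 or 0.9, started on average 0.1 year after the stop.

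**Step 3: approximation.** If replacement follows soon after the stop, the counted hazard is about λ + q·d, so

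HR ≈ (λ + q·d₁) / (λ + q·d₀).

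With λ = 0.10, q = 0.9, d₁ = 0.05 and d₀ = 0.06: (0.10 + 0.045) / (0.10 + 0.054) = 0.145 / 0.154 = 0.942. In the second arm about 0.054 / 0.154 = 35% of counted events are replacements.

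**Step 4: simulation** (300 trials per scenario, exponential times). The three values are for λ = 0.05, 0.10 and 0.20.

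| Discontinuation per year | Replaced | HR under SAP rule | Log-rank p < 0.05 |
|---|---|---|---|
| 0.06 vs 0.06 | 0, 50 or 90% | about 1.00 | 3-7% |
| 0.06 vs 0.05 or 0.04 | 0% | about 1.00 | 5-7% |
| 0.06 vs 0.05 | 50% | 0.947, 0.967, 0.981 | 24%, 17%, 12% |
| 0.06 vs 0.05 | 90% | 0.916, 0.943, 0.966 | 64%, 43%, 23% |
| 0.06 vs 0.04 | 50% | 0.890, 0.935, 0.963 | 81%, 49%, 21% |
| 0.06 vs 0.04 | 90% | 0.832, 0.888, 0.933 | over 99%, 93%, 67% |

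The approximation matches the simulation (0.942 against 0.943). The percentage with rescue moves too: at λ = 0.10 and 90% replacement it is 62.1% vs 60.0% (0.06 vs 0.05) and 62.1% vs 57.7% (0.06 vs 0.04).

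**Step 5: a second set of assumptions.** With λ = 0.06 or 0.10, 85% replacement, a mean delay of 3 months and 5.5-7.5 years of observation, 5% vs 6% discontinuation gives HR 0.93-0.95, and 5% vs 7% gives 0.87-0.91. Across two simulations, p < 0.05 in about 30-54% and 83-97% of trials respectively.

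**Step 6: censoring at study drug stop.** In every scenario of Step 4 this gives HR 0.99-1.01 and 3-8% rejection. That holds by construction, because drug stop was drawn independently of the need for rescue.

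**Step 7: dropping that independence.** Suppose failure of control has hazard 0.08 per year in both arms, unrelated discontinuation is 5% per year in both, and 20% vs 10% of failures are managed by stopping study drug and switching. Last-dose censoring then misses those failures: HR ≈ 0.08 × 0.80 / (0.08 × 0.90) = 0.064 / 0.072 = 0.889. Simulation gives 0.89, with p < 0.05 in about 70% of trials. The SAP rule gives HR 1.00 and about 5%.

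**The case against.** The strongest reply is that the SAP chose this rule openly. It says that rescue is not confined to time on study drug, which suits a treatment-policy measure and the intention-to-treat approach used elsewhere. Under that measure, more new therapy in one arm is a real difference. This stands, and it is why the planned analysis should stay. It does not explain why completers are closed at last dose, but that asymmetry is minor in itself: everyone leaves study drug at study end, and about 30 days of follow-up remain.

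Last-dose censoring is also not neutral. Protocol 4.2.1 says that some patients who need rescue outside the protocol-defined list should stop study drug; those may be failures of control, and Step 7 shows the resulting bias. This stands.

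A reader might infer that the SAP contradicts the protocol. The documents do not establish that: the narrower footnote belongs to the key secondary endpoints, and the amendment log says that a rescue definition was added for the tertiary endpoints, whose section is not in the public text. For the same reason the protocol-defined version of this endpoint may have a narrower event, although it shares the censoring rule.

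Therapy changes are recorded only if possible for stoppers on reduced contact, and short insulin courses do not count; both would shrink the effect. Discontinuation by arm is tabulated (SAP 7), as are antidiabetic drugs started after first intake (SAP 7.2), so an imbalance would be visible, though not linked to the rescue curve.

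**Conclusion.** The point holds as a limit on interpretation. As planned, the comparison measures rescue or replacement therapy combined, and a difference in discontinuation alone can produce an apparent difference: HR 0.87-0.95 at 5% vs 6-7% per year with 85% replacement. The mechanism follows from the text. The size rests on assumed rates; it is small at 50% replacement with a one-point gap in discontinuation (HR 0.95-0.98, rejection 12-24%) and absent when discontinuation is equal or no one is given a replacement. It is not a forecast for this trial.

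Two stronger readings are tempting. One is that the rule distorts the main conclusions. It does not: the endpoint is exploratory, the primary endpoint does not use rescue, and permanent discontinuers are non-responders for the second and third key secondary endpoints whatever the rescue rule (SAP 7.5.1). The other is that the analysis misstates durability of glycaemic control and should be replaced by last-dose censoring. The documents do not give this endpoint that label, and replacement would exchange one possible bias for another.

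**What to change.** 1. Keep the planned analysis and label it as rescue or replacement therapy.
2. In SAP 6.8.3 and 7.5.2.2.4, add a companion Kaplan-Meier and log-rank analysis, with the matching percentage, censored at last study drug intake (the final permanent stop) for all patients.
3. Tabulate first rescue before and after permanent stop by arm, with the reason for stopping.
4. State why the SAP window is wider than the wording of the protocol's key secondary footnote.

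The cost is one further censoring date, one further analysis, one table and a few lines of SAP text. The companion has fewer events and treats drug stop as censoring, which is informative when patients stop because control failed. The report should therefore show both versions together and interpret neither alone.

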#### *Primary endpoint sensitivity analyses*

Please refer to [Section 7.4.2](#).

#### *Endpoints of CV death, non-CV death and all-cause mortality*

A patient who did not die/died from another event will be censored at the latest date of the dates as described above, (for e.g. the primary endpoint) and the date of vital status (if alive)/ date last known to be alive (if LTFU)/ date of death (if died from another than event of interest).

Censoring rules and their application:

- 0-days censoring will be used for sensitivity analysis on TS (label: TS+0)
- 7-days censoring will be used for all adverse events - for hypoglycemia refer below (label: TS+7)
- 30-days censoring will be used for sensitivity analysis done on PPS (label: PPS) and OS (label: OS) and as additional sensitivity analysis regarding censoring on TS (label: TS+30)

All of the above mentioned x-day censoring rules will be handled as follows:

Patients who did not experience the event will be censored at the earliest date between the individual day of trial completion and x days after last intake of study drug. For this analysis events will be considered that occurred not later than x days after last intake of study drug, or until individual day of trial completion, whichever is earlier.

### *Silent MI*

A patient without this event will be considered censored at the last documented study visit\* as defined above.

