### *Endpoints based on laboratory data only*

Patients who already fulfil the respective condition at baseline are not considered in the number of patients at risk for this endpoint.

If a baseline laboratory measurement is not available for the parameter of interest, it is assumed that the patient did not experience the condition corresponding to the endpoint at baseline and the patient is included in the patients at risk for this endpoint.

Patients without an event and available post-baseline laboratory measurements will be considered censored at the date of last laboratory sampling of the corresponding parameter. Patients with missing baseline laboratory required to derive a change from baseline and patients without laboratory data following the baseline measurement will be censored on the day of randomisation or date of first study drug intake, respectively..

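### Time to silent MI counts off-drug contact without an ECG as event-free time: the rate is understated in both arms, and the hazard ratio is biased only if discontinuation differs between them

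*SAP*

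**What the plan says.** **Censoring.** The silent MI paragraph of SAP 6.8.3 reads: "A patient without this event will be considered censored at the last documented study visit". An asterisk points back to the general definition in the same section. That definition includes the date of trial completion, "defined as latest of date of last clinic visit, last telephone call, date of last contact if lost to follow-up", along with several event dates. No ECG date is named.

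**The general CV rule.** The block that holds this definition states the principle that "the censoring date should be the last date a patient was known to be free of an endpoint event", and adds: "Censoring is considered independent from study drug intake". Its heading, however, carves out certain endpoints: "except stand-alone endpoints of CV death, all-cause mortality, non CV-death and silent MI".

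**Start and event dates.** SAP 6.8.1 groups silent MI with laboratory endpoints: for "time to first silent MI and laboratory based endpoints, the date of first drug intake will be considered as starting point". SAP 6.8.2 dates the event from the investigator's report: "The time to the first silent MI is determined by the onset date of the adverse event defined as silent MI".

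**Laboratory endpoints.** SAP 6.8.3 says that event-free patients with post-baseline samples "will be considered censored at the date of last laboratory sampling of the corresponding parameter".

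**What the protocol provides.** Section 10.5 allows an MI to be called silent only if ECG criteria are met and the changes are new against earlier tracings. The Flow Chart plans ECGs at randomisation, week 16, every 48 weeks after that, and at end of treatment. Footnote N and Sections 3.1 and 3.3.4.1 place the end-of-treatment procedures at permanent discontinuation. They require no ECG after premature discontinuation, and contact may then shrink to one call a year plus one at study end.

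**The concern.** A telephone call can show that a patient is alive and has had no hospital admission. It cannot show that a silent infarct has not occurred. A patient who stops drug in year 2 and is phoned until year 7 adds up to five years to the time at risk, with no planned procedure that could add an event. The denominator runs on while the numerator largely stops.

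The protocol synopsis lists occurrence of and time to silent MI among the safety criteria. SAP 7.5.2.1 applies the primary Cox model to secondary and tertiary CV endpoints, so a hazard ratio is to be expected. At stake are an understated safety rate and, if patients leave drug faster in one arm, a ratio that flatters that arm.

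**Working it through.** **Inputs.** The documents state no silent MI rate, no discontinuation rate and no figure for this endpoint. Follow-up comes from Protocol 7.6: accrual 2 years and follow-up 5.4 years, so 5.4 to 7.4 years per patient, mean T = 5.4 + 2/2 = 6.4. As a check on that design, take event hazard h = -ln(1-0.018) and loss hazard l = -ln(1-0.015). Then 6000 x h/(h+l) x mean[1-exp(-(h+l)t)] over that range gives 628 events against the plan's 631. Assumed: permanent discontinuation d of 4-8% per year; 3-6 silent MIs per 1000 patient-years; 3000 patients per arm (Protocol synopsis); constant hazards.

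**Step 1: follow-up without an ECG.** With f the share of off-drug time still covered by ECGs,

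U = [1 - (1-exp(-dT))/(dT)] x (1-f).

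| d per year | dT | (1-exp(-dT))/(dT) | U, f = 0 | U, f = 0.5 |
|---|---|---|---|---|
| 0.04 | 0.256 | 0.882 | 11.8% | 5.9% |
| 0.05 | 0.320 | 0.856 | 14.4% | 7.2% |
| 0.06 | 0.384 | 0.830 | 17.0% | 8.5% |
| 0.08 | 0.512 | 0.783 | 21.7% | 10.9% |

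f = 0 also assumes no restarts, so it is an upper bound.

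**Step 2: effect on rate and ratio.** Because the event is rare, observed rate = true rate x (1-U), and a true ratio of 1.0 appears as (1-U for the arm with more discontinuation)/(1-U for the other arm).

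- 6% v 6%: each rate 17% too low at f = 0; ratio 1.0.
- 5% v 8%: 0.783/0.856 = 0.915 at f = 0; 0.961 at f = 0.5.
- 4% v 8%: 0.783/0.882 = 0.887 at f = 0; 0.947 at f = 0.5.

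**Step 3: against sampling error.** At 6 per 1000, true events per arm are 3000 x 6.4 x 0.006 = 115.2. For 5% v 8% at f = 0, about 98.6 and 90.2 are observed. SE of the log ratio = sqrt(1/98.6 + 1/90.2) = 0.146; bias = |ln 0.915| = 0.089, or 0.61 SE. Over 3-6 per 1000 and both pairs of discontinuation rates (94-211 events in total), the bias is 0.4-0.8 SE at f = 0 and 0.2-0.4 SE at f = 0.5.

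**Step 4: simulation.** True ratio 1.0, follow-up uniform from 5.4 to 7.4 years, the planned ECG schedule plus an ECG at discontinuation, and censoring unrelated to risk.

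- 1.5 million patients per arm, 6 per 1000, no off-drug ECGs, 5% v 8%: Cox ratio 0.910 under the current rule. It is 1.013 (rate ratio 1.000) when patients are censored at the last ECG and events are counted only to that date. Monte Carlo SE of the log ratio is about 0.007.
- 4% v 8%: 0.888 under the current rule with no off-drug ECGs; 1.009-1.024 under the last-ECG rule across the coverage scenarios.
- Last-ECG censoring that still counts events found on unrecorded ECGs (half of off-drug patients having such ECGs): 1.070 at 5% v 8% and 1.081 at 4% v 8%. Events and time at risk must therefore stop at the same date.
- A separate run (150,000 per arm, 5 per 1000, 5% v 8% with the faster-stopping arm as reference): rates of 4.27 and 3.83 per 1000 under the current rule, 4.99 and 4.91 with last-ECG censoring.

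**The case against.** **No rule is broken.** A reader might infer that the SAP contradicts its own principle of censoring at the last date known event-free. It does not: the heading of that block excepts silent MI, and the last-sample rule is limited to laboratory endpoints. Following everyone regardless of drug intake also fits the trial's intention-to-treat approach. What stands is an inconsistency of logic: silent MI shares its start date with the laboratory endpoints but not their censoring.

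**On-treatment rules exist.** SAP 6.8.3 applies 7-day censoring to all adverse events, and silent MI is dated as an adverse event. The same section describes a 30-day analysis on the treated set without limiting it to adjudicated endpoints. SAP 7.8.1.3.2 may yield an on-treatment incidence rate for some event types. But the silent MI paragraph is the specific rule for this time-to-event analysis. SAP 7.5.2.1 gives the 30-day analysis to adjudicated CV endpoints and all-cause mortality, and SAP 5.1 says silent MI is not confirmed by adjudication. No visible text plans a corrected hazard ratio.

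**Text is missing.** SAP 4 says the silent MI onset and censoring rules were updated, but the item explaining why is not visible; SAP 5.3 and 7.6 are not shown. One cannot conclude that nothing anywhere corrects this, which limits confidence.

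**ECGs are not forbidden.** Protocol 5.2.4 allows additional ECGs, and Section 3.3.4.1 allows unlimited restarts, which return patients to the schedule. This stands: the f = 0 figures are a ceiling.

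**Conclusion.** The point holds as a minor one, with moderate confidence. To the extent that off-drug time has no ECG, the plan counts it as event-free and understates the silent MI rate in both arms. Under the assumed 4-8% yearly discontinuation the understatement is at most 12-22%, or 6-11% at half coverage.

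A reader might also infer that the hazard ratio is biased. That follows only if permanent discontinuation differs between arms, and the documents give no sign either way. With equal discontinuation the ratio stays at 1.0; at 5% against 8% it moves to 0.91 (0.96 at half coverage), less than one standard error in every scenario examined. All these sizes rest on assumed rates.

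Nor does the point reach the main conclusions. This rule does not govern the primary or key secondary endpoints, and SAP 7.5.2 makes the other secondary analyses exploratory.

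**What to change.** Add one analysis of time to first silent MI and report it beside the current last-visit analysis. Either of two forms would do:

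- Censor event-free patients at their last recorded post-baseline 12-lead ECG (first drug intake if there is none), and count events only up to that date, in parallel with the laboratory rule.
- More simply, extend the existing 30-day treated-set rule to silent MI. This form was not simulated.

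In both cases report ECG-covered person-time by arm, and list separately any reported silent MI outside the covered period so that no safety event disappears.

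**Cost.** A short addition to SAP 6.8.2 and 6.8.3 and one extra analysis. Planned ECGs are stored centrally (Protocol 5.2.4), so their dates exist, and patients who complete treatment lose almost no follow-up because they have an end-of-treatment ECG. The first form also needs each reported silent MI matched to a recorded tracing, a link the visible documents do not describe; the second avoids this.

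**Downsides.** Patients who stop drug contribute less follow-up. If half of off-drug patients have only unrecorded ECGs, the first form leaves out about 8-13 of roughly 100-107 events per arm at 6 per 1000 patient-years. Censoring also becomes tied to discontinuation and may be informative, which the simulation did not examine; even without that, the last-ECG rule left a small residual the other way (up to 1.024). These are reasons to show both analyses rather than replace the current one.
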